A Data Safety Monitoring Board (DSMB), consisting of three individuals appointed by a third-party contractor, will meet as scheduled by this protocol to review safety throughout study conduct. Specifically, the DSMB will meet to assess the progress of the first five patients with mild symptoms after their second infusion, and a decision on continuation of study will be made prior to the third infusion (day 7). The same will occur for the first five patients experiencing severe symptoms after their second infusion, and a decision on continuation of study will be made prior to their third infusion (day 14). All other patients may be screened beforehand so that enrollment may occur once the committee declares it may resume. DSMB is scheduled for at least 3 meetings pertaining to this protocol: after the mild symptom group receives their second infusion, after the severe symptom group receives their second infusion, and at study midpoint. Additional meetings may be necessary, upon request from the Medical Monitor.

DSMB will review all deaths (to assure non-attribution), cases of anaphylaxis or suspected anaphylaxis, thromboembolic events, new malignancy/tumor, infections/hospitalizations (including unrelated to COVID-19 but due to underlying condition). DSMB will also review safety data at mid-point of the study.

Risks

Potential Risks of the Investigational Product and Clinical Investigation

Risks Associated with HB-adMSCs

Respiratory Risks:

A potential risk is that the infusion could initiate a VTE event with subsequent

cardiopulmonary sequelae of respiratory failure and/or right heart strain/failure. We plan to monitor oxygen saturation, and respiratory rate/work of breathing for the first 2 hours post-infusion. The patient will be examined for VTE events (clinical exam, oxygen saturation) during each infusion visit and at each follow-up visit.

Hepatic Risks:

The reticuloendothelial system can sequester immature blood elements, theoretically resulting in hepatic injury. An acute elevation of the AST/ALT hepatic enzymes $> 900 \text{ U/dl}$ within 72h post-infusions will be considered an infusion related adverse event. This level is based upon the organ system scoring definitions for moderate hepatic failure and corresponds to the CTCAE v4.03 Grade 3 adverse event. It is unlikely that "end vessel" micro-thrombosis would occur in the liver due to the dual blood supply of the liver and the lung is the first pass organ. A CMP will be obtained at follow-up visits.

Coagulation Cascade:

A coagulation panel will be obtained at screening, baseline, infusion and the follow-up visits. The patient will be monitored for the development of venous thromboembolic events (see pulmonary monitoring above) as well as for the development of clinical deep vein thrombosis (limb swelling, tenderness, discoloration).

The types of risk associated with HB-adMSCs are also stated in the Informed Consent Form (See ICF)

Minimization of Risks

Although the risk to subjects participating in the study is anticipated to be minimal, the clinician, at his/her discretion, will not collect data from those individuals for whom collection is judged to pose an unusually high risk of physical or mental harm or discomfort.

Participation in this study poses moderate risk to study personnel related to potential pathogens that may be present in the subject's specimens which are then expanded during the culture process. These risks will be minimized by adherence to the principles of universal precautions and by conducting the planned testing on blood from the subject at screening for particular pathogens of concern.

Personnel should wear appropriate personal protective equipment to avoid contact of the eyes or skin with hazardous materials or products derived from biological sources.

Subjects will be advised to follow current federal guidelines regarding COVID-19 such as the following:

- Clean and wash hands often with soap and water for at least 20 seconds upon arrival and exit of the site.
- Use hand sanitizer that contains at least 60% alcohol
- Avoid touching your eyes, nose, and mouth with unwashed hands
- Avoid close contact
- Adhere to social distancing guidelines and maintain at least 6' of distance with others

General procedures for study personnel include:

- Hands must be washed with soap and water for at least 20 seconds, if soap and running water are unavailable, an alcohol-based hand rub with at least 60% alcohol will suffice this action. Always wash hands that are visibly soiled.
- Avoid touching their eyes, nose or mouth.
- Healthcare workers will wear:
 - o Disposable Gowns
 - o Gloves
 - o Disposable N95 masks.
 - o Eye/face protection (e.g., goggles, face shield)
- Surfaces where subjects have been in contact will be disinfected 70% Isopropyl Alcohol.

Pre-infusion Medication

Prior to infusion, medications will be given to the participant as a precaution. Because the drug for this study is an allogeneic product, an allergy medication such as Loratadine (10mg), will be administered. The participant will be closely monitored for any signs of allergic reaction during the infusion and during the post-infusion monitoring period. No reactions are expected.

Potential Benefits

Subjects may benefit from their participation in the study by experiencing an overall feeling of well-being. Subjects enrolled in the study will be contributing to the advancement of science and to future investigations regarding stem cells and possible therapeutic applications, including treatment of respiratory diseases, specifically COVID-19.

Statistical Analysis

Determination of Sample Size

Sample size calculation was determined based upon the anticipated demand for treatment.

Null hypothesis- Efficacy

Treatment with HB-adMSCs does not cause changes in primary and secondary endpoints (listed below) for suspected Corona Virus Disease.

Alternative hypothesis-Efficacy

The alternative hypothesis for this study is that HB-adMSC treatment does result in changes from baseline values of primary and secondary endpoints in patients with suspected Corona Virus Disease.

Null hypothesis-Safety

Treatment with HB-adMSCs results in adverse or serious adverse events and/or detrimental changes in laboratory values, vital signs, weight, X-rays, EKG, or physical examination determined to be related to the study drug.

Alternative hypothesis-Safety

HB-adMSC treatment for COVID-19 does not result in adverse or serious adverse events and/or detrimental changes in laboratory values, vital signs, weight, X-rays, EKG, or physical examination determined to be related to the study drug.

Endpoints

The endpoints measured in this study are safety and clinical efficacy.

Safety is assessed by primary and secondary endpoints. Primary safety endpoints include incidence of adverse and serious adverse events. Secondary safety endpoints include incidence of specific adverse events including serious infections, infusion-related reactions, hepatotoxicity, heart failure, and cytopenias. Clinically significant changes in laboratory values, vital signs, weight, and physical examination results will also be measured.

Clinical efficacy is assessed by primary and secondary endpoints. Primary endpoints include the change from baseline in inflammatory markers (IL-6, D-dimer, C Reactive protein), time to clearing PCR test, change from baseline oxygenation, and time to return to room air (RTRA). Secondary endpoints include change from baseline of chest x-ray, change from baseline of CT scan, change from baseline of clinical laboratory values, adverse and serious adverse events, change in exploratory markers, and change in ordinal scale.

Analysis Population

Safety: All subjects receiving at least one infusion will be included for safety analysis.

Efficacy: All subjects receiving all four infusions will be included for efficacy analysis.

Additional sub-analysis will be performed comparing subjects receiving any other experimental treatment for COVID-19, to those who are not, in the following items:

- Change from baseline oxygenation
- Change from baseline chest x-ray
- Change from baseline CT scan
- Time to clearing PCR test
- Change from baseline inflammatory markers (IL-6, D-dimer, C Reactive protein)
- Change from baseline in IL-10
- Change from baseline in CD4:CD8 ratio
- Change from baseline in CD3⁺CD56⁺
- Change from baseline in VEGF
- Change from baseline in the 7-point ordinal scale

Demographic and Baseline Characteristics

Information describing subjects' gender, race/ethnicity, and age will be displayed in tables similar to the ones included below. The number and percent of the total sample population will be calculated for each demographic category.

Demographics	Female		Male		Both Genders	
Race/Ethnicity	N	%	N	%	Total	%
White						
Black or African American						
Hispanic or Latino						
Other (Specify)						
Total						

The mean, minimum, and maximum age at enrollment will be determined using standard calculations. The number and percent of total subjects in each age group will be calculated and reported.

Age at Enrollment	N	%
Mean		
Minimum		
Maximum		
	N	%
≥ 18 years		
18-21 years		
22-29 years		
30-39 years		
40-49 years		
50-59 years		
60-69 years		
70-79 years		
80-89 years		
90-99 years		
100-109 years		
Total	100	100
		%

Safety Analysis

The number, type, and description of all AEs and SAEs will be recorded and reported.

Efficacy Analysis

- change from baseline in oxygenation will be recorded and compared between placebo and treatment group; higher mean oxygen saturation in treatment group compared to placebo would indicate HB-adMSCs are effective in improving oxygenation compared to placebo
- change from baseline in inflammatory markers will be compared between placebo and treatment group; decreased values of D-dimer, IL-6, and CRP in treatment group compared to placebo group would indicate HB-adMSCs are effective in decreasing inflammation
- Time to clear PCR test; a decreased duration of time to achieve a clear PCR test in treatment group compared to placebo group would indicate that HB-adMSCs are effective in decreasing the length of time a subject is contagious
- Time to return to room air (RTRA); a decreased duration of time to achieve a return to room air (no supplementation) in treatment group compared to placebo group would indicate that HB-adMSCs are effective in decreasing the length of time a subject requires respiratory assistance or supplementation.

Interim Analysis

Interim analysis of all safety and efficacy data may be performed at any time deemed appropriate by the Sponsor. Data will be analyzed for internal informational purposes, reports, presentations, and manuscripts.

Study Management

Institutional Review Board and Informed Consent

Hope Biosciences Stem Cell Research Foundation is required to obtain IRB oversight of the research study. The IRB must be provided with Hope Biosciences Stem Cell Research Foundation -approved study protocol. Performance of the study may not begin until written evidence of IRB approval has been provided to Hope Biosciences Stem Cell Research Foundation. The conduct and performance of this study will be in accordance with applicable Hope Biosciences Stem Cell Research Foundation and Investigator responsibilities as described in Title 21 CFR 312, subpart D and other Good Clinical Practice guidance.

For each study patient, written informed consent will be obtained from the subject or Legally Authorized Representative (LAR) prior to any protocol-related activities. As part of this procedure, the Investigator or designated study staff must explain orally and in writing the nature, duration, and purpose of the study, and the action of the drug in such a manner that the patient is aware of the potential risks, inconveniences, or adverse effects that may occur. The patient should be informed that he/she may withdraw from the study at any time, and the patient will receive all information that is required by local regulations and ICH guidelines. The Investigator will provide the Sponsor or its representative with a copy of the IRB-approved ICF prior to the start of the study.

Investigator Responsibility

The PI is responsible for general administration of the study.

Before the study, the PI must:

- Sign the Protocol Signature Page him/herself and have all sub-investigators sign the Protocol Signature Page and return it to Hope Biosciences Stem Cell Research Foundation.
- Provide financial disclosures to Hope Biosciences Stem Cell Research Foundation for themselves and all sub-investigators participating in study conduct, per Title 21CFR 54

During the study, the PI must ensure that:

- The study is conducted ethically
- Case report forms (CRFs), including Subject ICFs, are provided with each transfer of data requiring informed consent.
- All other study forms are completed as instructed by Hope Biosciences Stem Cell Research Foundation.

In the case of completion or termination of the study or an Investigator's role in the study, or at Hope Biosciences Stem Cell Research Foundation request, all study materials must be returned to Hope Biosciences Stem Cell Research Foundation.

Case Report Forms/Electronic Data Records

As used in this protocol, the term CRF should be understood to refer to either a paper form or an electronic data record or both, depending on the data collection method(s) used.

Reports received by the site, or from the central laboratory should be printed, retained as source documentation and signed by the principal investigator, indicating which values are considered clinically significant and to be reported as AEs.

At all times, is it the PI's personal responsibility the completion, review, and approval of all CRFs, so as the accuracy and authenticity of all clinical and laboratory data entered on these CRFs. His/her signature will be required to attest that the information contained on the CRFs is true. Original CRFs should not be made available in any form to third parties, except for

authorized representatives of Hope Biosciences Stem Cell Research Foundation or appropriate regulatory authorities, without written permission from Hope Biosciences Stem Cell Research Foundation.

Source Documents

Source documents are considered to be all information in the original records and certified copies of original records of clinical findings, observations, data, or other activities in a clinical study necessary for the reconstruction and evaluation of the study.

Record retention

To maintain confidentiality, all laboratory specimens, evaluation forms, reports, and other records transmitted outside the clinical site will be identified by a patient's identification number. All study records, source medical records, and logs linking a patient's name to an identification number will be kept in a secure location. Clinical information will not be released without written permission of the patient/legal representative, except as specified in the ICF (e.g., necessary for monitoring by regulatory authorities or the Sponsor of the clinical study). The Investigator must also comply with all applicable privacy regulations (e.g., US Health Insurance Portability Accountability Act of 1996). The investigator and the study site will retain the essential documents (e.g., source documents such as medical records, signed ICF).

Essential documents should be retained at the study site for at least 15 years following completion of the study, or per regulatory obligations if longer, and thereafter destroyed only after agreement with the Sponsor. The Sponsor should notify the head of the study site in writing when the study-related records are no longer needed. The records should be managed by a responsible person appointed by the head of the study site.

Monitoring

The study will be monitored according to a Study Monitoring Plan (to be developed by Hope Biosciences Stem Cell Research Foundation and contracted CRO) to ensure that all procedures are conducted and documented properly according to the protocol, GCP, and all applicable regulatory requirements. On-site monitoring visits will be made at appropriate times during the study. Monitors include CRA and medical monitor, who must have direct access to source documentation in order to check the completeness, clarity, and consistency of the data recorded in the CRF for each subject. The Investigator will make available to the monitor source documents and medical records necessary to complete CRFs. In addition, the Investigator will work closely with the clinical monitor and, as needed, provide them appropriate evidence that the conduct of the study is being done in accordance with applicable regulations GCP guidelines.

Clinical Research Associate

A clinical research associate (CRA) will be continuously overseeing the conduct of the trial and ensuring it is at all times compliant with all authorities regulating the investigation including IRB, and FDA. The CRA will perform monitoring site visits on a monthly basis. The personnel

will be qualified by education, training, and experience to assume responsibility for the proper monitoring of the research study.

Audits

The investigator will allow study-related monitoring, audits, and inspections by the IRB, the Sponsor, or FDA, of all study related documents (e.g. source documents, regulatory documents, data collection instruments, study data etc.). Participation as an investigator in this study implies acceptance of potential inspection by government regulatory authorities and applicable Hope Biosciences compliance and quality assurance offices.

Protocol Deviations

An Investigator may not knowingly deviate from the study protocol without prior approval by Hope Biosciences and/or the IRB unless the deviations are necessary under emergency circumstances to protect the rights, safety, or well-being of human subjects or the scientific integrity of the clinical investigation. Deviations must be documented and promptly reported to Hope Biosciences and, if applicable, to the IRB providing oversight of the study.

Subject Stipends or Payments

Payment to research subjects for participation in studies is not considered a benefit that would be part of the weighing of benefits or risks.

Funding Source

Privately funded.

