Vital signs (body temperature, pulse, oxygen saturation, systolic and diastolic blood pressure measurements) will be evaluated at the visits indicated in the schedule of assessments. It is important that all vital signs be measured after the patient has been resting in a sitting position for at least 5 minutes. Blood pressure measurements are to be taken in the same arm for the duration of the study. Body weight (without coats and shoes) will be recorded whenever vital signs are recorded, and height (without shoes) will be recorded at screening only.

Vital sign measurements will be repeated if clinically significant or machine/equipment errors occur. Out-of-range blood pressure and pulse measurements will be repeated at the Investigator's discretion. Any confirmed, clinically significant vital sign measurements will be recorded as AEs and followed up as such.

Physical Examination

A complete physical examination (head, eyes, ears, nose, throat, heart, lungs, abdomen, skin, cervical and axillary lymph nodes, neurological, and musculoskeletal systems) will be performed at screening. In addition, medical history (including smoking history) will be recorded at screening.

A limited physical examination to verify continued patient eligibility and to follow up any change in medical history will be performed at the visits indicated in the schedule of

assessments. Symptom-driven physical examinations will be performed as clinically indicated at any study visit. All changes not present at baseline or described in the past medical history and identified as clinically noteworthy will be recorded as AEs.

Electrocardiogram

A 12-lead resting EKG will be obtained at screening and at the early discontinuation visit, if applicable. At screening, the Investigator will examine the EKG traces for signs of cardiac disease that could exclude the patient from the study. An assessment of normal or abnormal will be recorded and if the EKG is considered abnormal, the abnormality will be documented in the CRF. EKGs will be repeated if clinically significant abnormalities are observed or artifacts are present.

Clinical Laboratory Parameters

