The Investigator must review all laboratory reports and document the review. Any laboratory test result or change considered by the Investigator to be clinically significant should be considered an AE and recorded in the AE CRF. Clinically significant abnormal values occurring during the study will be followed until repeat test results return to normal, stabilize, or are no longer clinically significant.

Laboratory tests to be performed during the study:

Complete Blood Count with Differential	Natural Killer Cell Surface Antigen (CD3 ⁻ CD56 ⁺ Marker Analysis)
Complete Metabolic Profile	Il-10
Coagulation study (PTT/PT/INR)	CD4+ / CD8+ ratio
Urinalysis with pregnancy test	Creatine Kinase (CK)
C Reactive Protein	Troponin
Tumor Necrosis Factor alpha	Myoglobin (MB)
D-Dimer	VEGF
	Serum Ferritin

Adverse Events

An AE is any symptom, physical sign or disease that either emerges during the study or, if present at screening, worsens during the study, regardless of the suspected cause of the event. All medical and psychiatric conditions (except those related to the indication under study) present at screening will be documented in the medical history CRF. Changes in these conditions and new symptoms, physical signs, or diseases should be noted on the AE CRF during the rest of the study.

Clinically significant laboratory abnormalities should also be recorded as AEs. Surgical procedures that were planned before the patient enrolled in the study are not considered AEs if the conditions were known before study inclusion; the medical condition should be reported in the patient's medical history. Changes from baseline respiratory rate for non-ventilated subjects should also be considered as AE.

Serious Adverse Events (SAE)

A serious adverse event (SAE) is any AE that is:

- fatal
- life-threatening
- requires or prolongs hospital stay
- results in persistent or significant disability or incapacity
- Important Medical Events (IME): those events that may not result in death, be immediately life threatening, or require hospitalization. They may be considered a SAE when, based upon medical judgement, they may jeopardize the subject and may require intervention to prevent one of the other serious outcomes noted above. For example, drug overdose or abuse, a seizure that did not result in in-patient hospitalization, or intensive treatment of bronchospasm in an emergency department would typically be considered serious. (FDA, 21CFR312.32; ICH E2A and ICH E6)

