- Elevation or decrease in pulse of 20 bpm or more from baseline
- Change from baseline respiration rate in non-ventilated subjects

Study Alteration Rules

If any of the following events listed below occur, administration of the study drug will be immediately suspended. The Internal Monitoring Committee (IMC), presided by the Medical Monitor will meet to review the incident and its etiology. The committee determine if it is likely related to the drug, the infusion or unrelated. If the IMC along with the Medical Monitor agree that the SAE is unlikely or unrelated to the drug, the study will be continued. If the SAE appears to be definitely drug-related, the study will be stopped. If the SAE is probably or possibly linked to the drug, the IMC will determine the risk to future patients and decide if the study should proceed or be stopped.

Study Stopping Rules

The stopping rules listed below will trigger cessation of enrollment and potential study closure pending a comprehensive DSMB safety review.

1. Any infusion related death, deemed by PI to be associated or possibly associated with study drug.
2. Three or more of the same Grade 3 or higher AEs (judged by the investigator, medical monitor or sponsor), including infusion site reactions.
3. Any event which, in the opinion of the investigator, medical monitor or sponsor, contraindicates further dosing of additional subjects.
4. An infusion related, sustained (over 1 minute) episode of hypoxia (SaO₂ of less than 80%).
5. Any Grade 4-5 Adverse Event as defined in the NCI CTCAE v4.0 and determined to be temporally related to the HB-adMSC infusion by the Medical Safety Monitor and/or DSMB.

After such review, resumption of dosing may be considered, including consideration for any prophylactic interventions (e.g. antihistamines or corticosteroids for injection site reactions).

Medical Monitoring

Medical Monitor

It is the responsibility of the Principal Investigator to oversee the safety of the study at his/her site. This safety monitoring will include careful assessment and appropriate reporting of adverse events as noted above. At Hope Biosciences Stem Cell Research Foundation, [name], MD [contact] will be responsible for reviewing any reported AEs and SAEs to determine if changes to the study need to be made or if the study should be stopped for the protection of patients.

Data Safety Monitoring Board

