#### **7.2.4.2. Data Analytic Models**

All secondary endpoint efficacy measurements available at post-baseline at scheduled measurements (Visits 2 through 5 [infusions 1 through 4] for exploratory markers and clinical labs; Visits 2 through 6 [infusion 1 through end of treatment] for chest X ray, CT scan, and ordinal scale score) will be analysed in a generalized linear mixed model. The model will predict each outcome as a function of the interaction between the fixed factors treatment group and time, controlling for lower order effects of time and treatment group. Models will control for stratification variables (see [Covariates and Other Strata](#)), and subject will be included as random effects. AEs/SAEs and AE severity will be analyzed as dichotomous outcomes (whether patient exhibited AE/SAE at any time during the study). AE/SAE attribution to study drug will be analyzed as count outcomes. All models will control for stratification variables.

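### Any change in respiratory rate counts as an adverse event in non-ventilated patients, with no size, direction or significance condition, so the ever/never any-AE outcome may saturate in both arms

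*Protocol*

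**What the plan says.** The Adverse Events section of the protocol first defines an AE as something that emerges or worsens during the study. It then adds: "Changes from baseline respiratory rate for non-ventilated subjects should also be considered as AE". Nothing limits the size, direction or duration of the change, or requires clinical significance.

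The neighbouring rules do carry a condition:

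- Laboratory values (Adverse Events): "Clinically significant laboratory abnormalities should also be recorded as AEs".
- Vital signs (Vital Signs, Height, and Weight): "Any confirmed, clinically significant vital sign measurements will be recorded as AEs and followed up as such".
- Examination findings (Physical Examination): changes not present at baseline are AEs if clinically noteworthy.

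Respiratory rate is absent from the vital-sign list: "Vital signs (body temperature, pulse, oxygen saturation, systolic and diastolic blood pressure measurements) will be evaluated at the visits indicated". It has no row of its own in Table 2. Respiratory Risks names it for observation after dosing: "We plan to monitor oxygen saturation, and respiratory rate/work of breathing for the first 2 hours post-infusion". The same unqualified wording also appears in the Infusion Stopping Rules: "Change from baseline respiration rate in non-ventilated subjects".

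On analysis, the Endpoints text of the protocol states: "Primary safety endpoints include incidence of adverse and serious adverse events". The protocol's endpoint lists and SAP 2.1 and 7.2.1 place AE/SAE incidence under secondary endpoints. SAP 7.2.4.2 says that AEs/SAEs and AE severity "will be analyzed as dichotomous outcomes (whether patient exhibited AE/SAE at any time during the study"), and treats attribution to study drug as a count. SAP 8.1 adds summaries by severity and relation to treatment, and tables by system organ class and preferred term.

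**The concern.** Respiratory rate varies from reading to reading in a patient whose condition has not changed. If every departure from baseline is an AE, many non-ventilated patients acquire one from ordinary variation. A rate that falls as the patient recovers is also a change and, read literally, also an AE.

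An ever/never outcome is the form most easily damaged by this. Once a patient has one trivial AE, no later event can alter that patient's value. Both arms move toward 100%, and any real difference in AE incidence is compressed. The protocol also attaches this AE to a measurement whose baseline and schedule it does not define, so the number recorded will depend on how often the rate is taken and compared.

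**Working it through.** **No planned figure to reproduce.** The documents state no AE rate, power or respiratory-rate variability; the sample size rests on anticipated demand. From the documents come the arm sizes (60 active, 40 placebo), the ever/never outcome, and a two-sided 5% level for supplementary frequentist analyses. All else below is assumed.

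**Step 1: how often would a stable patient show a change?** Simulate a baseline and three later readings (as if on Days 3, 7 and 10) as normal values with a constant mean, rounded to the recording step. Find the share of patients with at least one later reading different from baseline, and the share with at least one above it. Ranges run over a within-patient SD of 1 to 3 breaths/min.

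| Recording step (breaths/min) | Any change | Rises only |
|---|---|---|
| 1 | 97% to 99.9% | 60% to 71% |
| 2 | 84% to 99% | 46% to 66% |
| 4 | 51% to 94% | 26% to 55% |

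With 15 later readings instead of three, any change reaches 85% to 100% over the same SDs and steps. Three may be few: Instructions for Administration sets seven vital-sign time points per infusion (four during, three after), if the rate is taken with them.

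**Step 2: what does this do to the any-AE comparison?** Let p be a patient's chance of an AE without the clause, and q the chance of an AE from the clause alone, assumed equal in both arms and independent of other AEs. Then

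any-AE rate = 1 − (1 − p)(1 − q), and difference between arms = (p_active − p_placebo)(1 − q).

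Take assumed true rates of 60% active and 30% placebo:

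- q = 0: 60% vs 30%, difference 30 points.
- q = 0.50: 1 − 0.4 × 0.5 = 80% vs 1 − 0.7 × 0.5 = 65%, difference 15 points.
- q = 0.90: 1 − 0.4 × 0.1 = 96% vs 1 − 0.7 × 0.1 = 93%, difference 3 points.
- q = 0.95: 98.0% vs 96.5%, difference 1.5 points.

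**Step 3: power as a yardstick.** The main analysis is Bayesian; power only shows how much information is lost. For 60 vs 40 patients, two-sided 5%, power = Φ[(difference − 1.96 × SE0)/SE1], with SE0 from the pooled rate and SE1 from the separate rates.

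- q = 0: pooled rate 0.48; SE0 = √(0.48 × 0.52 × (1/60 + 1/40)) = 0.102; SE1 = √(0.6 × 0.4/60 + 0.3 × 0.7/40) = 0.096; power = Φ(1.04) = 85% (exact Fisher 83%).
- q = 0.90: pooled rate 0.948; SE0 = 0.0453; SE1 = 0.0476; power = Φ(−1.24) = 11% (Fisher 6.5%).
- q = 0.50: power 39%. q = 0.95: power 8%.

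Starting from 50% vs 20% or 80% vs 50%, power is about 88% without the clause, 36% to 52% at q = 0.50 and 10% to 15% at q = 0.90.

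**Step 4: what is untouched?** A rate change adds nothing to SAE incidence unless it itself meets a seriousness criterion. An assumed 35% vs 10% SAE difference keeps 84% power whatever q is.

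Here q applies to all patients in an arm. Ventilated patients are outside the clause, so q equals the Step 1 share times the non-ventilated fraction, which the documents do not give.

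**The case against.** **The general definition governs.** An AE must emerge or worsen, and a rate falling toward normal does neither. This is a fair reading, and it lowers the share affected to 26% to 71%. But the added sentence speaks of changes without direction, and even rises from ordinary variation would inflate the outcome substantially.

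**The rule may be deliberate.** Respiratory failure after a thromboembolic event is a named infusion risk, and the significance rule for vital signs does not plainly govern a measurement outside its list. This stands as an explanation of why the sentence exists. It does not explain why this measurement alone has no condition.

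**Stronger readings that the documents do not support.**

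- A reader might infer that the primary safety endpoint cannot separate the arms. SAE incidence is also named as primary and is not saturated; severity, attribution and coded-term summaries remain; and the endpoint lists and the SAP class AE incidence as secondary.
- A reader might infer that almost every patient will have such an AE. That depends on recording to single breaths, counting falls as well as rises, and readings that the vital-sign section does not list.
- A reader might infer that differing site practice biases the comparison. Site is a stratification variable and model covariate (SAP 5.4.1), arms are randomised, and evaluators are blinded, so uneven recording mostly adds noise.

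**Conclusion.** The concern holds for the ever/never any-AE outcome only. The sentence on respiratory rate lacks the condition that the protocol applies to laboratory values, listed vital signs and examination findings. Followed literally, it inflates any-AE incidence in both arms and can count improvement as an event.

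The size cannot be fixed from the documents. Under the assumptions above, 51% to 99.9% of non-ventilated patients would show a change, or 26% to 71% if only rises count. If the clause alone gave 90% of patients an AE, an assumed 30-point difference would shrink to 3 points and power would fall from 85% to 11%; at 50% the loss is smaller but still large. The actual effect depends on how the rate is recorded, how many patients are ventilated and how sites read the sentence. This should be corrected, but the rest of the safety evaluation remains able to distinguish the arms.

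**What to change.** 1. **Protocol, Adverse Events:** reconcile the respiratory-rate sentence with the clinically significant standard that the protocol already uses for recording laboratory and vital-sign AEs.
2. **Protocol, Vital Signs, Height, and Weight:** add respiratory rate to the recorded vital signs, so that its baseline and visits are defined.
3. **SAP 7.2.4.2 and 8.1:** add an any-AE summary that excludes AEs based solely on a respiratory-rate change, with such AEs identified before treatment codes are released. If AEs have already been collected under the present sentence, this is the part that can still help.

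The cost is a one-sentence amendment with CRF guidance, an addition to the vital-sign list, and one extra table. The downside is slightly less capture of minor respiratory changes in the headline AE figure; the individual listings in SAP 8.1 and 8.3 would still show them.

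The line with the same unqualified wording in the Infusion Stopping Rules must be reconciled separately by those responsible for clinical conduct. No threshold is proposed here.
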